6.1.2.2 Administration of Investigational Product (baseline, Day 0)

The investigator shall administer the investigational product (VM202) on the following sites of a subject's both lower limbs. The number of injections depending on the administration site of VM202 shall be 56 intramuscular injections in total with 28 injections for 3 sites on the left and right lower limbs, respectively. See "Appendix 3. Administration Method of Investigational Product" for details.

- Peroneus longus muscle 6 injections for left peroneus longus muscle and 6 injections for the right peroneus longus muscle
- Gastrocnemius muscle 12 injections for the left gastrocnemius muscle and 12 injections for the right gastrocnemius muscle
- Tibialis anterior muscle 10 injections for the left tibialis anterior muscle and 10 injections for the right tibialis anterior muscle

6.1.2.3 After Administration of Investigational Product (baseline, Day 0)

The following shall be performed after administration of the investigational product.

Vital signs

Vital signs including blood pressure (measurement shall be taken with the subject in a sitting position after resting for at least 10 minutes prior to measurement), temperature, heart rate per minute, and respiratory rate per minute shall be measured. The measurement results shall be recorded in the subjects' case report forms. This shall be performed at Visit 1 (screening) and throughout the clinical study every time a subject makes a visit (on the drug administration days consisting of Visits 2, 3, 4, and 5, it shall be performed both prior to administration and 2 ± 1 hours after administration). However, if there is a subject with abnormal findings in the test at Visit 3 (Day 14), a follow-up test may be performed at Day 30 depending on the decision of the principal investigator.

Adverse event assessment

Localized adverse events shall be checked at 2 ± 1 hours after administering the investigational product and on the day after administration.

Scheduled MRI and electroneurography

This shall be scheduled to be performed on the same day as Visit 7 (Day 270) prior to discharge.

6.1.3 Visit 3 (Second Administration, Day 14 ± 5)

6.1.3.1 Before Administration of Investigational Product

The following shall be performed prior to administering the investigational product.

Adverse event assessment

Information on newly developed or worsened adverse events, or adverse events that disappeared since the last visit shall be collected.

Body measurement (weight measurement)

A subject's weight shall be measured at Visit 1 and throughout the clinical study every time a subject makes a visit (shall be performed prior to administering the investigational product at Visits 2, 3, 4, and 5).

Complete blood cell count

This shall be performed at Visit 1 and throughout the clinical study every time a subject makes a visit (shall be performed prior to administering the investigational product at Visits 2, 3, 4, and 5). However, if there is a subject with abnormal findings in the test at Visit 3 (Day 14), a complete blood cell count and a general blood chemistry test may be performed at Day 30 depending on the decision of the principal investigator. The complete blood cell count items are as follows:

WBC, RBC, Hb, Hct, MCV, MCH, MCHC, PLT, ESR, MPV, differential count of WBC (Band neutrophil,

Segmented neutrophil, Eosinophil, Basophil, Lymphocyte, Monocyte)

General blood chemistry test

This shall be performed at Visit 1 and throughout the clinical study every time a subject makes a visit (shall be performed prior to administering the investigational product at Visits 2, 3, 4, and 5). However, if there is a subject with abnormal findings in the test at Visit 3 (Day 14), a complete blood cell count and a general blood chemistry test may be performed at Day 30 depending on the decision of the principal investigator. Since a blood glucose test is included, the subject shall maintain an 8-hour fasting state prior to the test. The general blood chemistry test items are as follows:

total protein, albumin, globulin, A/G ratio, cholesterol, total bilirubin, AST, ALT, fasting glucose, BUN, creatinine, estimated GFR, Ca²⁺, phosphate, Na⁺, K⁺, Cl⁻, CRP, triglyceride, HDL- cholesterol, LDL-cholesterol

Urinalysis with microscopy

This shall be performed at Visit 1 and throughout the clinical study every time a subject makes a visit (shall be performed prior to administering the investigational product at Visits 2, 3, 4, and 5). However, if there is a subject with abnormal findings in the test at Visit 3 (Day 14), urinalysis with microscopy may be performed at Day 30 depending on the decision of the principal investigator.

The urinalysis items are as follows:

Color, turbidity, specific gravity, pH, albumin, glucose, ketones, bilirubin, blood, urobilinogen, nitrite, leukocyte esterase, microscopy (RBC, WBC, casts)

Vital signs

Vital signs including blood pressure (measurement shall be taken with the subject in a sitting position after resting for at least 10 minutes prior to measurement), temperature, heart rate per minute, and respiratory rate per minute shall be measured. The measurement results shall be recorded in the subjects' case report forms. This shall be performed at Visit 1 (screening) and throughout the clinical study every time a subject makes a visit (on the drug administration days consisting of Visits 2, 3, 4, and 5, it shall be performed both prior to administration and 2 ± 1 hours after administration). However, if there is a subject with abnormal findings in the test at Visit 3 (Day 14), a follow-up test may be performed at Day 30 depending on the decision of the principal investigator.

Concomitant medications survey

The brand names and ingredient names of concomitant medications shall be surveyed at every visit and recorded in the case report form. All medications and treatments administered within 6 months before Visit 1 (screening) shall be surveyed. Previous medications and previous

treatments shall be defined as all previously collected medications and treatments before Visit 2 (first administration of investigational product). Concomitant medications and treatments shall refer to all medications that have been administered at least once starting from Visit 2 (first administration of investigational product) and throughout the clinical study. The categories of collected medications and treatments shall follow this definition. The following shall also be surveyed for each medication:

- Brand name
- Indications for medication administration (reason for administration)
- · Dose/strength, administration route, number of administrations
- Start and discontinuation dates of administration (whether to continue when the clinical study is terminated)

Neurologic exam

Along with the assessments for the patient's sensation and motor symptoms, the following neurologic exam (motor system: muscle strength; sensory system: nociception, pallesthesia) shall be performed.

Table 11. Neurologic exam items and procedures

Test Item	Procedure
Muscle	Reduced muscle strength is referred to as weakness or paresis, and the loss of strength is referred to as paralysis. To measure the muscle strength of limbs, the flexion (C5-6) and extension of wrist joint, extension of wrist (C6-8), grasping test (C7-T1), abduction of finger (C8-T1, ulnar nerve), and opposition of thumb (C8-T1, median nerve) shall be tested in the upper limbs. For the strength of intrinsic hand muscles, only the two muscles of the abductor pollicis brevis (APB) and the first dorsal interosseous (FDI) shall be evaluated, and the stronger of the two shall be scored. In the lower limbs, the flexion (L2-L4), adduction (L2-L4), and extension (S1) of hip joint, the extension (L2-L4) and flexion (L4-S2) of knee, as well as the dorsiflexion (L4-5) and plantar flexion (S1) of ankle shall be tested. The results of performing a muscle strength test of the limbs in a subject shall be indicated using the Medical Research Council (MRC) grade*. * MRC grade (Motor power) O: Complete paralysis I: Flicker of contraction possible II: Movement possible if gravity eliminated III: Movement possible against some resistance V: Power normal (it is not normally possible to overcome a normal adult's power)
Nociception	Stimulation shall be applied by alternately using tools with a dull end and a sharp end, and it shall be verified whether these can be distinguished. When comparing the left and right sides of the body, stimulation shall be applied to the same sites. Then, the subject shall be asked whether the sensations are the same.
Pallesthesia	Vibration shall be applied to a low-pitched tuning fork (a Rydel-Seiffer tuning fork shall be used), and this shall be placed on the distal joints of the hands and feet to verify that the subject feels the vibrating sensation. Pallesthesia is

the first sensation lost in peripheral nerve disorders.

6.1.3.2 Administration of Investigational Product

The investigator shall administer the investigational product (VM202) on the following sites of a subject's both lower limbs. The number of injections depending on the administration site of VM202 shall be 56 intramuscular injections in total with 28 injections for 3 sites on the left and right lower limbs, respectively. See "Appendix 3. Administration Method of Investigational Product" for details.

- Peroneus longus muscle 6 injections for left peroneus longus muscle and 6 injections for the right peroneus longus muscle
- Gastrocnemius muscle 12 injections for the left gastrocnemius muscle and 12 injections for the right gastrocnemius muscle
- Tibialis anterior muscle 10 injections for the left tibialis anterior muscle and 10 injections for the right tibialis anterior muscle

6.1.3.3 After Administration of Investigational Product

The following shall be performed after administration of the investigational product.

Vital signs

Vital signs including blood pressure (measurement shall be taken with the subject in a sitting position after resting for at least 10 minutes prior to measurement), temperature, heart rate per minute, and respiratory rate per minute shall be measured. The measurement results shall be recorded in the subjects' case report forms. This shall be performed at Visit 1 (screening) and throughout the clinical study every time a subject makes a visit (on the drug administration days consisting of Visits 2, 3, 4, and 5, it shall be performed both prior to administration and 2 ± 1 hours after administration). However, if there is a subject with abnormal findings in the test at Visit 3 (Day 14), a follow-up test may be performed at Day 30 depending on the decision of the principal investigator.

Adverse event assessment

Localized adverse events shall be checked at 2 ± 1 hours after administering the investigational product and on the day after administration.

Day 30 ± 7 (shall be performed only if follow-up testing is required) 6.1.4

This shall be performed only for subjects who are determined by the principal investigator to take short-term follow-up testing due to abnormal findings in the

PRT NO: VMCMT-001 Confidential 2021.06.07 84 / 85

hematology test at Visit 2 (Day 14).

Adverse event assessment

Information on newly developed or worsened adverse events, or adverse events that disappeared since the last visit shall be collected.

Body measurement (weight measurement)

A subject's weight shall be measured at Visit 1 and throughout the clinical study every time a subject makes a visit (shall be performed prior to administering the investigational product at Visits 2, 3, 4, and 5).

Complete blood cell count

This shall be performed at Visit 1 and throughout the clinical study every time a subject makes a visit (shall be performed prior to administering the investigational product at Visits 2, 3, 4, and 5). However, if there is a subject with abnormal findings in the test at Visit 3 (Day 14), a complete blood cell count and a general blood chemistry test may be performed at Day 30 depending on the decision of the principal investigator. The complete blood cell count items are as follows:

WBC, RBC, Hb, Hct, MCV, MCH, MCHC, PLT, ESR, MPV, differential count of WBC (Band neutrophil, Segmented neutrophil, Eosinophil, Basophil, Lymphocyte, Monocyte)

General blood chemistry test

This shall be performed at Visit 1 and throughout the clinical study every time a subject makes a visit (shall be performed prior to administering the investigational product at Visits 2, 3, 4, and 5). However, if there is a subject with abnormal findings in the test at Visit 3 (Day 14), a complete blood cell count and a general blood chemistry test may be performed at Day 30 depending on the decision of the principal investigator. Since a blood glucose test is included, the subject shall maintain an 8-hour fasting state prior to the test. The general blood chemistry test items are as follows:

total protein, albumin, globulin, A/G ratio, cholesterol, total bilirubin, AST, ALT, fasting glucose, BUN, creatinine, estimated GFR, Ca²⁺, phosphate, Na⁺, K⁺, Cl⁻, CRP, triglyceride, HDL-cholesterol, LDL-cholesterol

Urinalysis with microscopy

This shall be performed at Visit 1 and throughout the clinical study every time a subject makes a visit (shall be performed prior to administering the investigational product at Visits 2, 3, 4, and 5). However, if there is a subject with abnormal findings in the test at Visit 3 (Day 14), urinalysis with microscopy may be performed at Day 30 depending on the decision of the principal investigator.

The urinalysis items are as follows:

Color, turbidity, specific gravity, pH, albumin, glucose, ketones, bilirubin, blood, urobilinogen, nitrite, leukocyte esterase, microscopy (RBC, WBC, casts)

Vital signs

Vital signs including blood pressure (measurement shall be taken with the subject in a sitting position after resting for at least 10 minutes prior to measurement), temperature, heart rate per minute, and respiratory rate per minute shall be measured. The measurement results shall be recorded in the subjects' case report forms. This shall be performed at Visit 1 (screening) and throughout the clinical study every time a subject makes a visit (on the drug administration days consisting of Visits 2, 3, 4, and 5, it shall be performed both prior to administration and 2 ± 1 hours after administration). However, if there is a subject with abnormal findings in the test at Visit 3 (Day 14), a follow-up test may be performed at Day 30 depending on the decision of the principal investigator.

Concomitant medications survey

The brand names and ingredient names of concomitant medications shall be surveyed at every visit and recorded in the case report form. All medications and treatments administered within 6 months before Visit 1 (screening) shall be surveyed. Previous medications and previous treatments shall be defined as all previously collected medications and treatments before Visit 2 (first administration of investigational product). Concomitant medications and treatments shall refer to all medications that have been administered at least once starting from Visit 2 (first administration of investigational product) and throughout the clinical study. The categories of collected medications and treatments shall follow this definition. The following shall also be surveyed for each medication:

- Brand name
- Indications for medication administration (reason for administration)
- Dose/strength, administration route, number of administrations
- Start and discontinuation dates of administration (whether to continue when the clinical study is terminated)

Neurologic exam

Along with the assessments for the patient's sensation and motor symptoms, the following neurologic exam (motor system: muscle strength; sensory system: nociception, pallesthesia) shall be performed.

Table 12. Neurologic exam items and procedures

Test Item	Procedure
Muscle strength	Reduced muscle strength is referred to as weakness or paresis, and the loss of strength is referred to as paralysis. To measure the muscle strength of limbs, the flexion (C5-6) and extension of wrist joint, extension of wrist (C6-8), grasping test (C7-T1), abduction of finger

(C8-T1, ulnar nerve), and opposition of thumb (C8-T1, median nerve) shall be tested in the upper limbs. For the strength of intrinsic hand muscles, only the two muscles of the abductor pollicis brevis (APB) and the first dorsal interosseous (FDI) shall be evaluated, and the stronger of the two shall be scored.

In the lower limbs, the flexion (L2-L4), adduction (L2-L4), and extension (S1) of hip joint, the extension (L2-L4) and flexion (L4-S2) of knee, as well as the dorsiflexion (L4-5) and plantar flexion (S1) of ankle shall be tested.

The results of performing a muscle strength test of the limbs in a subject shall be indicated using the Medical Research Council (MRC) grade*.

- * MRC grade (Motor power)
- 0: Complete paralysis
- I: Flicker of contraction possible
- II: Movement possible if gravity eliminated
- III: Movement against gravity but not resistance
- IV: Movement possible against some resistance
- V: Power normal (it is not normally possible to overcome a normal adult's power)

Nociception

Stimulation shall be applied by alternately using tools with a dull end and a sharp end, and it shall be verified whether these can be distinguished. When comparing the left and right sides of the body, stimulation shall be applied to the same sites. Then, the subject shall be asked whether the sensations are the same.

Pallesthesia

Vibration shall be applied to a low-pitched tuning fork (a Rydel-Seiffer tuning fork shall be used), and this shall be placed on the distal joints of the hands and feet to verify that the subject feels the vibrating sensation. Pallesthesia is the first sensation lost in peripheral nerve disorders.

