- 10) Urine or serum pregnancy test At Visit 1 (screening), urine or serum pregnancy tests shall be performed in females of childbearing potential (from post-menarche females to females ≥ 50 years of age within 1 year of menopause, or from post-menarche females to females < 50 years of age within 2 years of menopause). However, patients with surgical menopause (hysterectomy, bilateral oophorectomy, etc.) or who underwent sterilization surgery (bilateral tubal ligation, bilateral tubectomy) may be excluded. Menopause refers to the state after 1 year of amenorrhea.
- 11) Electrocardiogram: The electrocardiogram to be performed at Visit 1 (screening) may use results within 4 weeks before Visit 1 (screening).
- 12) Concomitant medications survey: All medications and treatments administered within 6 months before Visit 1 (screening) shall be surveyed. Previous medications and previous treatments shall be defined as all previously collected medications and treatments before Visit 2 (first administration of investigational product). Concomitant medications and treatments shall refer to all medications that have been administered at least once starting from Visit 2 (first administration of investigational product) and throughout the clinical study. The categories of collected medications and treatments shall follow this definition. Whether the medications and treatments being administered should be continued shall be

- investigated at each visit.
- 13) MRI leg: The muscles of lower limbs shall be imaged, and the fatty infiltration level of the leg muscles injected with the investigational product shall be measured and evaluated as fat content value (%) at one level for each muscle. Considering the schedule, etc., of the institution, it shall be performed optionally at the early termination visit, and if it is not performed, the reasons shall be recorded in the case report form.
- 14) Adverse event assessment: At Visits 3, 4, and 5, an assessment of adverse events that have occurred since the last visit shall be performed prior to administering the investigational product, and localized adverse events shall be assessed at 2 ± 1 hours after administering the investigational product, as well as on the day after administration.

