- 15) Hospitalization: Subjects shall be hospitalized on the day before administration of the investigational product and their vital signs shall be measured. If they are not hospitalized, vital signs may be omitted, and the hospitalization day in the case report form shall be recorded the same as the test day prior to administration.
- 16) After administration: Vital signs and adverse events shall be assessed at 2 ± 1 hours after administering the investigational product. The presence or absence of localized adverse events shall be verified on the day after administering the investigational product.

Glossary of Abbreviations

AE Adverse Event

AESI Adeverse Events of Special Interest

AFO Ankle Foot Orthosis

ALS Amyotrophic Lateral Sclerosis
ALT Alanine Transaminase (SGTP)

Anti-HCV Hepatitis C Antibodies

AST Aspartate Transaminase (SGOP)

BMI Body Mass Index

BUN Blood Urea Nitrogen

CBC Complete Blood cell Count

cDNA Complementary Deoxynucleic Acid

CLI Critical Limb Ischemia

CMAP Compound Muscle Action Potential

CMT Charcot-Marie-Tooth disease

CMT1A Charcot-Marie-Tooth disease subtype 1A

CMTNS-v2 Charcot-Marie-Tooth Neuropathy Score Version 2

COX-1 Cyclooxygenase-1
COX-2 Cyclooxygenase-2
CRF Case Report Form

CRO Contract Research Organization

DM Data ManagementDMP Data Management PlanDNA Deoxyribonucleic Acid

DPN Diabetic Peripheral Neuropathy
DSMB Data Safety Monitoring Board

EDC Electronic Data Capture

EKG Electrocardiogram

FDS Functional Disability Scale
GCP Good Clinical Practice
HbcAb Hepatitis B core antibody
HbsAb Hepatitis B surface antibody
HbsAg Hepatitis B surface antigen

HBV Hepatitis B Virus

HCG Human Chorionic Gonadotrophin

HCT Hematocrit

HCV Hepatitis C Virus

HED Human Equivalence Dose

Hgb Hemoglobin

HGF Hepatocyte Growth Factor

HIV Human Immunodeficiency Virus

HMSN Hereditary Motor and Sensory Neuropathy
HTLV Anti-Human T-Cell Lymphotropic Virus

IHD Ischemic Heart Disease

IL-6 Interleukin-6

IND Investigational New Drug
IRB Institutional Review Board
ISR Injection Site Reaction

ITT Intent-to-Treat

KGCP Korea Good Clinical Practice

LOCF Last Observation Carried Forward Analysis

MCH Mean Corpuscular Hemoglobin

MCHC Mean Corpuscular Hemoglobin Concentration

MCV Mean Corpuscular Volume

MedDRA Medical Dictionary for Regulatory Activities

MPV Mean Platelet Volume

MRI Magnetic Resonance Imaging
mRNA Messenger Ribonucleic Acid

NCI-CTCAE National Cancer Institute-Common Terminology Criteria for Adverse Events

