- 13) MRI leg: The muscles of lower limbs shall be imaged, and the fatty infiltration level of the leg muscles injected with the investigational product shall be measured and evaluated as fat content value (%) at one level for each muscle. Considering the schedule, etc., of the institution, it shall be performed optionally at the early termination visit, and if it is not performed, the reasons shall be recorded in the case report form.
- 14) Adverse event assessment: At Visits 3, 4, and 5, an assessment of adverse events that have occurred since the last visit shall be performed prior to administering the investigational product, and localized adverse events shall be assessed at 2 ± 1 hours after administering the investigational product, as well as on the day after administration.
- 15) Hospitalization: Subjects shall be hospitalized on the day before administration of the investigational product and their vital signs shall be measured. If they are not hospitalized, vital signs may be omitted, and the hospitalization day in the case report form shall be recorded the same as the test day prior to administration.
- 16) After administration: Vital signs and adverse events shall be assessed at 2 ± 1 hours after administering the investigational product. The presence or absence of localized adverse events shall be verified on the day after administering the investigational product.

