6.1.5 Visit 4 (Third Administration, Day 90 ± 7)

6.1.5.1 Before Administration of Investigational Product

The following shall be performed prior to administering the investigational product.

Adverse event assessment

Information on newly developed or worsened adverse events, or adverse events that disappeared since the last visit shall be collected.

Body measurement (weight measurement)

A subject's weight shall be measured at Visit 1 and throughout the clinical study every time a subject makes a visit (shall be performed prior to administering the investigational product at Visits 2, 3, 4, and 5).

Complete blood cell count

This shall be performed at Visit 1 and throughout the clinical study every time a subject makes a visit (shall be performed prior to administering the investigational product at Visits 2, 3, 4, and 5). However, if there is a subject with abnormal findings in the test at Visit 3

(Day 14), a complete blood cell count and a general blood chemistry test may be performed at Day 30 depending on the decision of the principal investigator.

The complete blood cell count items are as follows:

WBC, RBC, Hb, Hct, MCV, MCH, MCHC, PLT, ESR, MPV, differential count of WBC (Band neutrophil, Segmented neutrophil, Eosinophil, Basophil, Lymphocyte, Monocyte)

General blood chemistry test

This shall be performed at Visit 1 and throughout the clinical study every time a subject makes a visit (shall be performed prior to administering the investigational product at Visits 2, 3, 4, and 5). However, if there is a subject with abnormal findings in the test at Visit 3 (Day 14), a complete blood cell count and a general blood chemistry test may be performed at Day 30 depending on the decision of the principal investigator. Since a blood glucose test is included, the subject shall maintain an 8-hour fasting state prior to the test.

The general blood chemistry test items are as follows:

total protein, albumin, globulin, A/G ratio, cholesterol, total bilirubin, AST, ALT, fasting glucose, BUN, creatinine, estimated GFR, Ca²⁺, phosphate, Na⁺, K⁺, Cl⁻, CRP, triglyceride, HDL-cholesterol, LDL-cholesterol

Sample collection for retrospective biomarker study

The serum of subjects shall be collected and stored frozen at -70°C. All blood samples are stored with unique numbers for retrospective biomarker study after all personal information is deleted.

Urinalysis with microscopy

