6.2 Assessment Items

1) Safety and tolerability assessment items

- (1) Adverse events
 - All adverse events that manifest after administration of the investigational product shall be collected.
 - At Visits 3, 4, and 5 (2nd, 3rd, and 4th administration sessions of the investigational product), adverse events shall be assessed and collected before and after administration of the investigational product.
- (2) Laboratory tests (complete blood cell count/general blood chemistry/urinalysis tests)
- (3) Vital signs

2) Efficacy assessment items

- (1) Changes in severity of disease
 - CMTNS-v2 (Charcot-Marie-Tooth Neuropathy Score version 2)
 - FDS (functional disability scale)
- (2) Changes in lower limb function
 - ONLS (overall neuropathy limitation score) leg scale
 - 10MWT (10-meter walk test)
- (3) Changes in fatty infiltration level of lower limb muscles
 - MRI leg
- (4) Nerve regeneration potential
 - CMAP (compound motor nerve action potential)
 - SNAP (compound sensory nerve action potential)
 - NCV (nerve conduction velocity)
- (5) HGF antibody generation by VM202

7 Adverse Event

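### The Protocol contradicts itself on whether the 2-hour post-dose check covers all adverse events or only local ones, and the next-day check names only local ones

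*Protocol*

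**What the plan says.** Five places in the Protocol bear on what is asked after an injection session.

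- **Visit text, 6.1.2.3, 6.1.3.3, 6.1.5.3 and 6.1.6.3.** The adverse event instruction is the same after all four doses: "Localized adverse events shall be checked at 2 ± 1 hours after administering the investigational product and on the day after administration". Vital signs are also measured at 2 ± 1 hours.
- **Schedule footnote 14** (Synopsis and 6.1), for Visits 3, 4 and 5: "localized adverse events shall be assessed at 2 ± 1 hours after administering the investigational product, as well as on the day after administration".
- **Schedule footnote 16** (Synopsis and 6.1), attached to the post-dose column of every dosing visit. For the 2-hour check: "Vital signs and adverse events shall be assessed at 2 ± 1 hours after administering the investigational product". For the next day: "The presence or absence of localized adverse events shall be verified on the day after administering the investigational product".
- **Section 6.2**, repeated in the Synopsis under the primary endpoint. In general: "All adverse events that manifest after administration of the investigational product shall be collected". For Visits 3, 4 and 5: "adverse events shall be assessed and collected before and after administration of the investigational product".
- **Section 7.4.3.** All adverse events from administration to the end of the trial are collected, and the principal investigator teaches subjects to report every reaction.

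A general enquiry about changes since the previous visit is scheduled at Visits 3 to 7, before dosing where a dose is given. The Day 30 visit (6.1.4) has one too, but takes place only if the principal investigator wants follow-up of abnormal Day 14 tests.

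**The concern.** Site staff following the visit-by-visit text would ask about the injection sites at both post-dose contacts. Staff following footnote 16 would ask about everything at 2 hours and about the injection sites the next day. Both would be complying with the same protocol.

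The protocol itself expects reactions away from the injection site. Table 17 lists allergic reaction, dyspnea and facial swelling among the effects of intramuscular injection. Table 18 lists nausea and diarrhoea among the events seen in 5% or more of earlier study subjects. Brief events of this kind are more likely to be recorded if someone asks within a day than if the subject must recall them at a visit weeks later.

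SAP 4.7 summarises treatment-emergent events, drug reactions and events of special interest with exact intervals. Injection site reactions are one of the special-interest categories. Nothing in the SAP separates events found by direct questioning from those reported spontaneously, so the balance of local and systemic events in the report could partly reflect what was asked.

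**Working it through.** **Step 1. Scope of each contact, by source.**

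| Source | 2 ± 1 h check | Next-day check |
|---|---|---|
| 6.1.2.3, 6.1.3.3, 6.1.5.3, 6.1.6.3 | local | local |
| Footnote 14 (Visits 3–5) | local | local |
| Footnote 16 (all doses) | adverse events, no limit | local |
| Section 6.2 (Visits 3–5) | adverse events after dosing, no limit, no clock time | not mentioned |

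The first column contains a contradiction. The second is consistent: each source that defines a next-day check names local events only.

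**Step 2. Count of post-dose contacts.** 4 doses × 2 contacts = 8 per subject. Local events are named at all 8. Systemic events are covered at 0 of 8 under the visit text and at 4 of 8 under footnote 16.

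**Step 3. Time from a dose to the next general enquiry.** The documents print no such interval, so it is derived from the schedule. Inputs (day ± window): Visit 2, Day 0; Visit 3, 14 ± 5; Day 30 visit, 30 ± 7; Visit 4, 90 ± 7; Visit 5, 104 ± 7; Visit 6, 180 ± 7. Nominal gap = later day − earlier day. Range = nominal gap ± (sum of the two windows).

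| From | To | Nominal (days) | Range (days) |
|---|---|---|---|
| Dose 1 (Visit 2) | Visit 3 | 14 − 0 = 14 | 14 ± 5: 9–19 |
| Dose 2 (Visit 3) | Visit 4 | 90 − 14 = 76 | 76 ± 12: 64–88 |
| Dose 2 (Visit 3) | Day 30, if held | 30 − 14 = 16 | 16 ± 12: 4–28 |
| Dose 3 (Visit 4) | Visit 5 | 104 − 90 = 14 | 14 ± 14: 0–28 |
| Dose 4 (Visit 5) | Visit 6 | 180 − 104 = 76 | 76 ± 14: 62–90 |

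The 0–28 range for dose 3 is what the windows alone permit, each being counted from Day 0.

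**Step 4. How much of the gap comes from the word localized.** Suppose both contacts asked about all events. After doses 2 and 4 the last general enquiry would then fall one day after dosing, and the next 76 − 1 = 75 days later. Wider questions therefore cover roughly the first day; the remaining interval is visit spacing.

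**Step 5. What one subject weighs.** With 12 subjects, one subject is 1/12 = 8.3 percentage points. One affected subject gives 1/12, exact 95% interval about 0.2% to 38.5%; if that subject's event goes unrecorded the result is 0/12, interval 0% to 26.5%. This shows sensitivity to a single missed event. It does not estimate how many would be missed.

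**The case against.** The strongest reply is that the local check adds to general collection and does not replace it. No instruction says that only local events may be recorded. Section 7.2.2 defines an injection site reaction by a 24-hour limit and 7.4.3.1 makes it an event of special interest, so a targeted check at 2 hours and the next day has a purpose of its own. Around it stand the collection of all events in 6.2 and 7.4.3, vital signs at 2 hours (relevant to allergic reaction and dyspnea), unscheduled visits, and a general enquiry before doses 2, 3 and 4.

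Much of this stands, and it rules out three stronger readings that a reader might infer.

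- *Systemic reactions are first asked about 76 days after doses 2 and 4.* Footnote 16 calls for an unrestricted check at 2 hours. The interval applies with certainty only to reactions that start after that check, and some subjects may be asked at Day 30.
- *A reaction can go unasked before the next dose.* Visits 3, 4 and 5 each require a general enquiry before dosing, and no dose follows the fourth. The weakness is recall, not a missing question.
- *The systemic event rate is biased low by a known amount.* No missed-event rate is given. Under-capture is a plausible direction and no more.

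The reply leaves two things unanswered. The sources still disagree about the 2-hour check, and none requires a general question the next day. Spontaneous reports and unscheduled visits depend on the subject coming forward; the Day 30 visit is triggered by test results, not by symptoms.

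**Conclusion.** The point holds as an internal contradiction on the 2-hour check, together with a next-day contact that names only local events. For systemic reactions starting after the 2-hour check, the next mandatory general enquiry is nominally 14 days after doses 1 and 3 and 76 days after doses 2 and 4. If sites follow the visit text, the same applies to systemic reactions already present at 2 hours, apart from what vital signs or the subject reveal.

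The likely consequence is less complete capture of early systemic events than of local ones, in the primary endpoint. The size cannot be computed from the documents. The conclusion assumes that direct questioning finds events that unprompted reporting and later recall do not, and that staff treat the visit text as their working instruction. If the site in practice asks an open question at both contacts, the effect on the data is nil and only the wording needs repair.

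**What to change.** Reconcile 6.1.2.3, 6.1.3.3, 6.1.5.3, 6.1.6.3 and footnotes 14 and 16 (in both the Synopsis and section 6.1) with section 6.2, so that the existing 2 ± 1 hour and next-day contacts ask about all adverse events, local and systemic. The targeted injection site check can remain within that. Section 6.2 supports the wider scope after dosing but is silent on the next day, so the next-day change should be made explicitly.

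The cost is a few more questions at contacts that already take place; no visit is added. The gain is limited to roughly the first day after each dose.

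The real downside is timing. Section 5.7.1 states that enrollment is complete. If some doses have already been given, new wording would change ascertainment partway through a 12-subject study. In that case the study report should state which contacts asked about local events only, and interpret the local and systemic rates with that in view. If all doses have been given, only this disclosure remains to be made.
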